5. MATERIAL AND METHODS

A) TYPE OF STUDY

This doctoral thesis consists of a study which is defined as a randomized, experimental and controlled clinical trial, with three parallel groups, prospective, longitudinal and with a blind evaluation for the researcher.

B) MATERIALS AND/OR TECHNIQUES USED

Regarding the materials / physical resources necessary to carry out this study, they are stated below.

- Room at the Miguel Naranjo Center for the first consultation and different evaluations.
- Office with a stretcher and the equipment required for a physiotherapy consultation.
- Certified medical device (EPI Alpha, Barcelona, Spain)
- Needles for the application of the EP technique.
- Ultrasound

As for the techniques used, different ones will be used for each study group and are developed below.

1. Working methodology of the High Intensity Percutaneous Electrolysis group.

A sterile, disposable stainless steel needle of different lengths depending on the area to be treated will be connected to the EP device. The gauge of these needles will be 0.25 mm. A current of 3 mA will be applied 3 times for a duration of 3 seconds each. To avoid bias, the technique will be performed for 90 seconds, just like the low-intensity treatment group, and in the last 20 seconds the current will be applied with the parameters described above. Three sessions will be applied divided into 3 consecutive weeks. This parameter has been previously used in recent studies (10,20).

2. Working methodology of the low intensity percutaneous electrolysis group

This technique will be performed with the same instrument as the high intensity technique. It differs from the previous treatment group in that the current intensity in this case will be 0.3 mA for 90 seconds. Similarly, 3 sessions will be applied divided into 21 consecutive days (21,22).

3.Simulated Percutaneous Electrolysis working methodology.

The needle and the EP device will be connected in the same way as for the other treatment groups. The needle will be inserted without reaching the lesion area and the characteristic sound of turning on the EP machine will be made. It will last 90 seconds and at no time will the galvanic current be applied. The same aseptic precautions will be applied, in addition to the same final hemostasis guidelines and the same post-treatment guidelines provided to all the other subjects in the study.

C) STUDY POPULATION

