The study population for this clinical trial will be completed by a sample of approximately 50 adults between the ages of 18 and 65 who have suffered a muscle injury in the medial gastrocnemius. The researchers will consider a tear in the medial gastrocnemius if this pathology had any of the following characteristics:

- Medical diagnosis of fibrillar tear in the inner calf.
- Physiotherapeutic diagnosis of muscle tear after ultrasound examination.
- Pain in the GM area that coincides with a previously diagnosed fibrillar tear.

Theinclusion criteria for the following study will be the following:

- Age over 18 years and under 65 years.
- Muscle tear in the medial gastrocnemius.
- With pain in the area of the injury.

- That you have been informed of the purpose, as well as the risks and benefits of this study and that you have provided your written consent to participate in the trial.
- Available for tracking.

The exclusion criteria are listed below:

- Active rehabilitation in other musculoskeletal pathology.
- Belenophobia
- Immunosuppression.
- Uncontrolled metabolic diseases.

D) STUDY VARIABLES:

1. Sociodemographic variables

- 1. Age (years).
- 2. Sex.
- 3. Weight (kg).
- 4. Height (m).
- 5. Tear size (cm)
- 6. Location, Since the medial gastrocnemius is a peripheral myoconnective region, we will distinguish between tendon, myotendinous, muscular and myofascial injuries (23).
- 7. Chronicity: This section sets out the time since the rupture occurred. It is considered to be part of the 2nd week if it occurred before 14 days, 3rd week if it occurred before 21 days, 4th week if less than 28 days have passed, and between 4 and 8th week if less than 56 days have passed.

2. Outcome variables.

1. EVA pain scale.

The evaluation of the pain of the participants both in an upright position (without contraction) and in contraction will be carried out through a Verbal Scale

Pain score of 10 points (0 = no pain, 10 = maximum tolerable pain). Subjects will be asked to numerically rate the pain in a neutral standing position and in a position with both heels raised, also commonly known as standing on their toes. In the latter position, a score of 10 will be given if the subjects are unable to maintain this position for at least one full lift.

2. Kinesiophobia questionnaire (TSK-11SV).

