The assessment of fatigue in this muscle group will be carried out by performing a heel-raise test (4) at the beginning and at the end of the test for all participants who have completed it. The test consists of placing the patient on one leg and with the help of a metronome at a speed of 40 beats per minute (Garmin Fénix 5/5S), he is asked to raise his heel (4). When the patient is unable to raise his heel for 3 consecutive beats, fatigue will be considered. Light support on a wall is authorized to save the patient's balance.

E) WORK PLAN.

[figure not shown]
The study will be carried out as follows;

- Phase I or initial: Pre-study consultations will begin. Any patient who calls the
 centre to express their wish to take part in the study or who comes to the
 centre naturally will be given an appointment for a consultation with the
 principal investigator. All patients who strictly meet the eligibility criteria will
 be offered to participate in the study.
- Phase II or treatment: The entire treatment will be applied by the same physiotherapist (principal investigator) according to the randomization table that will be made so that each patient is assigned a treatment; high intensity EP, low intensity EP or sham EP. The treatment will be carried out in three sessions divided into three

weeks (days 1, 7 and 14) The person in charge of collecting the data will not be aware of which treatment each patient receives and will collect the data before the interventions.

• *Phase III or evaluation:*Patients will be scheduled for appointments two weeks after the last visit (day 28). The data from this last visit will be collected by the same person as the previous ones. All tests will be performed to collect the data and they will be given a telephone number in case they have any adverse events.

Study timeline.

F) ANALYSIS PLAN

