6 DATA COLLECTION SHEETS

DATA COLLECTION SHEET

SOCIODEMOGRAPHIC VARIABLES

Identifier:	Birthdate:
Sex:	Height (m):
Weight (kg):	Chronicity of the injury (weeks):
Location of the lesion:	Tear size (cm):

MYOFASCIAL PAIN VAS SCALE 1-10.

	PRE-INTERVENTION	POST-INTERVENTION
PAIN AT REST		
PAIN IN LOAD		

KINESIOPHOBIA LEVEL

	PRE-INTERVENTION	POST-INTERVENTION
AVERAGE SCORE		

ANKLE DORSIFLEXION RANGE WITH KNEE IN FULL EXTENSION

	PRE-INTERVENTION	POST-INTERVENTION
ANGLE		

MUSCLE FATIGUE OF THE TRICEPS SURAE

	PRE-INTERVENTION	POST-INTERVENTION
TEST SCORE		

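### Time since rupture is collected but enters neither the stated allocation nor the stated analysis, which costs precision and leaves a real chance of uneven arms

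*Protocol*

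**What the plan says.** All references are to the Protocol.

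- **Design and size (section 5, A and C).** The trial is described as "with three parallel groups, prospective, longitudinal and with a blind evaluation for the researcher", in "a sample of approximately 50 adults between the ages of 18 and 65". No allocation ratio is given.
- **Eligibility (section 5, C).** The injury criterion is "Muscle tear in the medial gastrocnemius" with pain in the area. There is no lower or upper limit on time since rupture.
- **Chronicity (section 5, D, sociodemographic variable 7).** For the youngest band, "It is considered to be part of the 2nd week if it occurred before 14 days". The oldest is "between 4 and 8th week if less than 56 days have passed". A tear older than that is eligible but has no band.
- **Data sheet (section 6).** The field reads "Chronicity of the injury (weeks)". No injury date is recorded.
- **Allocation (section 5, E, Phase II).** Each patient receives "high intensity EP, low intensity EP or sham EP" "according to the randomization table that will be made so that each patient is assigned a treatment". Strata, blocks and ratio are not mentioned. One investigator sees the candidates and gives all treatments.
- **Analysis (section 5, F).** Continuous outcomes are compared by a bivariate Student t test and ordinal ones by Mann-Whitney. No covariate is named.

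**The concern.** The protocol itself treats injury stage as relevant. Its justification section separates acute from chronic stages and contrasts normal regeneration with a fibrotic scar. Yet a tear a few days old and one at eight weeks can enter the same trial and be compared at day 28 as if interchangeable.

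If recent tears are expected to improve more without treatment over four weeks, two things follow. Uneven arms can make an active arm look better or worse than sham in this one trial. Even with even arms, the unexplained spread from chronicity stays in the error term and widens the confidence interval. A three-arm trial of about 50 people has little precision to spare, and the variable that would recover some of it is already being collected.

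**Working it through.** **Inputs.** From the protocol: about 50 patients, three arms, no strata named, unadjusted tests. Assumed, because the protocol is silent: equal allocation (17/17/16); a two-way split into fresh (under 28 days) and old; a fresh share *p* of 20-50% (by symmetry, 50-80% gives the same results). The protocol has no sample-size calculation and no figure for imbalance, so there is nothing of its own to reproduce.

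**Step 1. Typical gap between two arms.** SD of the difference in fresh share = √(2p(1−p)/17).
- p = 0.2: √(2 × 0.16/17) = 0.137
- p = 0.5: √(2 × 0.25/17) = 0.171

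A chance gap of 14 to 17 percentage points is thus one standard deviation.

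**Step 2. Chance of a given gap from sham in at least one active arm.** With *i* fresh tears among the n_s sham patients, and binomial counts in each arm, sum over *i*:

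P = Σ Bin(i; n_s, p) × [1 − P(|J/n_h − i/n_s| < t) × P(|K/n_l − i/n_s| < t)]

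Here J and K are the fresh counts in the high-intensity and low-intensity arms, of sizes n_h and n_l. The two figures in each cell are for sham as a 17-person arm and as the 16-person arm.

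| Fresh share | gap ≥ 20 points | gap ≥ 30 points |
|---|---|---|
| 20% | 22% / 22% | 4% / 5% |
| 30% | 34% / 35% | 9% / 10% |
| 40% | 41% / 45% | 11% / 13% |
| 50% | 43% / 47% | 12% / 14% |

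The overall ranges are 22-47% and 4-14%. For one given comparison of 17 v 17 they are lower: 13-23% for 20 points and 2-6% for 30 points.

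**Step 3. What a gap does to the estimate.** Shift = gap × prognostic difference δ. The protocol gives no δ. With δ assumed at 1-3 pain points, a 30-point gap shifts the arm difference by 0.30 × 1 = 0.3 to 0.30 × 3 = 0.9 points. With an assumed SD of 2, the standard error of an arm difference is 2 × √(2/17) = 0.69, and the 95% half-width is 1.96 × 0.686 = 1.34. The shift lies within ordinary sampling error.

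**Step 4. Precision lost by not adjusting.** Variance ratio, unadjusted to adjusted = 1 + δ²p(1−p)/SD², with SD = 2 within strata.
- δ = 1, p = 0.3: 1 + 0.21/4 = 1.05
- δ = 2, p = 0.3 to 0.5: 1 + 4 × 0.21/4 = 1.21 to 1 + 4 × 0.25/4 = 1.25
- δ = 3, p = 0.5: 1 + 9 × 0.25/4 = 1.56

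The unadjusted variance is 5-56% larger for a share of 30-50%. At a share of 20% the range is 4-36%.

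**Step 5. After stratifying at 28 days.** In simulated allocations, the largest gap from sham was 5.9 points (1/17) with blocks of 3. It was 12.5 points (2/16) with blocks of 6 or with a random mix of 3 and 6. A gap of 15 points or more never occurred. Without strata its chance is 44-63%.

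**The case against.** The strongest reply is that the protocol is silent on strata rather than against them. The table is still to be made, and a randomisation plan or SAP that is not shown may define it. That stands: the protocol cannot be said to have ruled out stratification. It does not answer the analysis section, which names its tests, and those tests are unadjusted.

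A second reply is that chance imbalance does not bias a randomised comparison on average and is already covered by the confidence interval. That also stands. The loss is in precision, and at the low end it is only about 5%.

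Third, no passage gives a recovery rate by weeks since injury, so the prognostic weight of chronicity is an expectation. That is why it is shown here as an assumed range, and for pain only.

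Fourth, small blocks within strata could let the investigator who enrols and treats, and who knows past assignments, work out some of the next ones. This is a fair cost of stratifying and has to be met by concealment. It does not apply to adjustment in the analysis.

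A reader might go further and infer that a large imbalance is likely, or that it would be as large as the effect sought. The documents support neither. A gap of 20 points or more stays below even odds across the assumed range, and one of 30 points or more is uncommon. The protocol states no target effect, SD or power with which a shift could be compared.

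**Conclusion.** The point holds as a matter of efficiency and robustness, not of validity. A baseline variable that the trial already collects, and whose relevance its own rationale suggests, has no role in the stated allocation or analysis.

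The risk of a 20-point gap from sham in at least one comparison is roughly one in five to just under one in two. The precision cost could be trivial or substantial, depending on how strongly chronicity drives recovery. The imbalance figures rest on equal allocation, a two-way split at 28 days and a fresh share of 20-50%. The variance figure also rests on an assumed 1-3 point effect and an SD of 2. The trial remains interpretable without the change. Adjustment can still be specified later, but stratification is no longer available once enrolment starts.

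**What to change.** 1. **Analysis plan (section 5, F).** Replace the unadjusted t test with a linear model of the day-28 outcome on arm, adjusted for chronicity. This is the main change. Cost: one extra model term.
2. **Data sheet (section 6).** Record the injury date instead of weeks, so that days since injury can be used and the days before day 14 are not merged. Cost: one field exchanged for another.
3. **Randomisation table (section 5, E).** When it is made, stratify it by chronicity (under 28 days; 28 days or more, a boundary already in the protocol's bands), with permuted blocks of randomly varying size 3 and 6. This holds the gap from sham to at most about 12.5 points. Cost: two lists instead of one, and the stratum must be known before an assignment is released. Because the same unblinded investigator enrols and treats, block sizes and upcoming assignments must be concealed from that person, for instance by having someone else hold the lists.

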For the coding and analysis of the data, the SPSS 22.0 statistical program will be used. For the treatment of quantitative variables, tables of absolute and relative frequencies will be prepared; in the case of quantitative variables, frequency measures will be used to determine their distribution, also obtaining their mean and standard deviation. The Kolmogorov-Smimov test will be performed to check the normality of the distribution. For the comparison of means of the continuous dependent variables, a bivariate statistical analysis will be performed using the Student T test. In the case of ordinal dependent variables, a comparison of medians will be performed using the bivariate analysis applying the Mann-Whitney test. In all cases, a 95% confidence interval and a precision error of 5% will be established.

G) LIMITATIONS AND POSSIBLE BIASES OF THE STUDY

This study has a number of limitations that should be taken into account when designing future research.

Firstly, the sample of participants will include people aged between 18 and 82, which may lead to biases due to the different variables that can influence different ages. It should also be noted that all people who participate will do so voluntarily by calling the centre to ask about the study or by showing up at the centre, so the possibility of bias due to voluntary participation must be taken into account.

It should also be noted that only one follow-up consultation will be carried out two weeks after the last intervention, so we will not have information on the behaviour of the variables beyond that date and therefore we will not be able to analyse the long-term results. It would be interesting to add post-intervention evaluations, as well as to study possible long-term recurrences.

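### The only adverse-event step in the visible protocol is a telephone number given at day 28, and the data sheet has no adverse-event field, so no systematic recording of harms by arm is planned during treatment

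*Protocol*

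**What the plan says.** **Visits.** Protocol section 5.E, Phase II, places the three sessions in three "weeks (days 1, 7 and 14"). Phase III adds one evaluation: "Patients will be scheduled for appointments two weeks after the last visit (day 28"). Section 5.G confirms that "only one follow-up consultation will be carried out two weeks after the last intervention".

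**Adverse events.** The one visible mention is in Phase III. After saying that all tests are done at that visit, the protocol adds that "they will be given a telephone number in case they have any adverse events". The Phase I and Phase II paragraphs have no contact step and no question about harms.

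**Forms and analysis.** The sheet in section 6, headed "DATA COLLECTION SHEET", holds identification and sociodemographic items, then pre and post cells for pain, kinesiophobia, dorsiflexion and fatigue. Its outcome blocks run from "MYOFASCIAL PAIN VAS SCALE 1-10" to "MUSCLE FATIGUE OF THE TRICEPS SURAE". The outcome variables in section 5.D are the same four, and the analysis plan in section 5.F mentions no summary of harms.

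**Exposure.** All arms are needled. For sham, section 5.B says: "The needle will be inserted without reaching the lesion area".

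**The concern.** The period in which procedure-related events are most likely to arise is the two weeks of sessions and the days just after them. The plan places its adverse-event step at the end of that period, on the last scheduled visit, and the form filled in along the way has nowhere to enter an event.

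This is a trial of two current intensities against sham, and the summary in section 2 says that it will inform how these injuries are treated and managed. A comparison of intensities that reports benefit without tolerability gives the clinician half of what is needed. The protocol itself foresees procedural risk: section 5.B refers to asepsis, hemostasis and post-treatment guidance, and section 5.C requires participants to have been told of the risks.

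A later statistical analysis plan could specify a harms table, but it cannot tabulate what was never collected. What is asked, and when, is settled by the protocol and its form.

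**Working it through.** **Step 1: timing.** Inputs are the session days (1, 7, 14) and the evaluation day (28), both from section 5.E. Intervals from each session to the visit at which the number is mentioned:

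- first session: 28 − 1 = 27 days
- second session: 28 − 7 = 21 days
- third session: 28 − 14 = 14 days

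Section 5.G allows for one follow-up consultation, so an event telephoned in after day 28 has no later visit at which it could be entered.

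**Step 2: the form.** Counting fields on the section 6 sheet:

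- identification and sociodemographic: identifier, birthdate, sex, height, weight, chronicity, location, tear size = 8
- outcome rows: pain at rest, pain in load, kinesiophobia, dorsiflexion angle, fatigue score = 5, each with pre and post cells, so 5 × 2 = 10 cells
- adverse events: 0

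**Step 3: exposure.** About 50 participants (section 5.C) × 3 sessions = about 150 needling sessions with no planned place to note a reaction.

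**Step 4: what recording could show (illustration only).** The protocol gives no event rate and no allocation ratio. Assume equal allocation, 50 / 3 ≈ 17 per arm, and a range of true rates p per participant. The chance of at least one event in an arm is 1 − (1 − p)^17:

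| Assumed true rate p | Calculation | Chance of at least one event |
|---|---|---|
| 1% | 1 − 0.99^17 | 16% |
| 5% | 1 − 0.95^17 | 58% |
| 10% | 1 − 0.90^17 | 83% |
| 20% | 1 − 0.80^17 | 98% |

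A fairly common event would therefore probably occur in an arm. A rare one might well not.

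**Step 5: what recording could not show.** On the same 17 per arm:

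- With no events observed, the one-sided 95% upper limit is 1 − 0.05^(1/17) = 0.162, so rates up to about 16% would remain compatible with the data.
- Fisher's exact test at two-sided 5% has about 19% power for 10% against 30%, and about 39% for 10% against 40%.

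The counts would be descriptive.

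**The case against.** **The contact may be given earlier, out of sight.** Section 9 says that a consent form is provided when treatment begins and that it covers the relevant aspects of the study. The consent pages are not available, the work-plan figure is missing, and the post-treatment guidance is mentioned without its content. A number handed over at the last visit could also simply be cover for the time after visits end. A reader might infer that patients have no way to report a problem during treatment. The documents do not support that, because an earlier contact cannot be ruled out. This part of the objection stands. It does not reach the form: a contact number is not a recording field.

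**Events might still be written down.** Participants are seen on days 7, 14 and 28, and one physiotherapist treats them throughout. A reader might conclude that harms would go unrecorded; the text shows only that no recording is planned. Informal notice is possible, but it is not systematic and cannot be relied on to be even across arms.

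**There may be another sheet.** The section 6 heading is plural, one sheet is visible, and section numbering passes from 6 to 8. A separate adverse-event form cannot be excluded outright, but nothing in the work plan, outcome list or analysis plan refers to one.

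**Safety is not an objective, and a harms table belongs in the analysis plan.** Section 4 indeed asks about pain, kinesiophobia, fatigue and mobility only, and leaving the layout of a table to the analysis plan is normal. Collection is a different matter, and the protocol fixes it.

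**Recording would not settle which intensity is better tolerated.** Correct, as step 5 of the working shows. A reader might take the gap as costing the trial a tolerability comparison. At this size no formal comparison was within reach; what is lost is the description.

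**Conclusion.** The point holds in a limited form. In the visible protocol, the adverse-event step comes 27, 21 and 14 days after the three sessions, and the sheet has 18 fields and cells (8 + 10), none for adverse events. No systematic recording of harms by arm is planned during treatment.

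This rests on the visible text being the whole of the plan for data collection. An earlier contact in the consent form would remove the timing half and leave the recording half untouched. The probabilities rest on 17 per arm and on assumed rates, neither of which the protocol states; the conclusion does not depend on them.

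The change should be made before enrolment. It does not affect the efficacy comparison, but events not recorded at the time are hard to recover reliably afterwards.

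**What to change.** 1. State in section 5.E that the contact number is given before the first session, or confirm that the consent form already does so.
2. Add an adverse-event row to the section 6 sheet: event, date, severity, relation to the procedure.
3. Split the recording between two people. The blinded data collector asks about events since the last session on days 7, 14 and 28. The treating physiotherapist notes reactions during or just after each session on days 1, 7 and 14. The collector cannot do the second task, because section 5.E has that person collect data ahead of each intervention.
4. Report counts descriptively by randomised arm, with no formal test between arms.

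**Cost.** Slightly more form work and one small table, with no extra visits or staff. The drawback is that immediate reactions are recorded by someone who knows the allocation, so they are best shown separately from events elicited by the blinded collector.

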4. OBJECTIVES

RESEARCH QUESTION:In adults with medial gastrocnemius injury, how effective is percutaneous electrolysis in terms of pain, kinesiophobia, fatigue and mobility?

HYPOTHESIS:The working hypothesis of the present study is the following: "The application of percutaneous electrolysis (PE) at high intensity (3 mA) and at low intensity (0.3 mA) will be more effective in the treatment of muscle tears of the internal calf than the simulated application of percutaneous electrolysis in adult subjects."

GENERAL OBJECTIVE:To determine the effectiveness of an intervention consisting of the application of percutaneous electrolysis in different doses versus the application of a simulated intervention in adults who present a muscle tear in the internal calf.

SPECIFIC OBJECTIVES:

- 1. To analyze the effectiveness of Percutaneous Intratisular Electrolysis, in its different forms. intensities, applied to the internal gastrocnemius muscle, in terms of myofascial pain in patients participating in the study, both at rest and during muscle contraction, measured using the visual analog scale (VAS).
- 2. To analyze the effectiveness of a simulated intervention applied to the internal gastrocnemius muscle, in terms of myofascial pain in patients participating in the study, both at rest and during muscle contraction, measured through the visual analog scale (VAS).
- 3. Evaluate and compare the effect of the protocols on the level of kinesiophobia of the participating subjects through the TSK-11SV questionnaire.
- 4. To demonstrate whether there are differences in muscle fatigue of the affected muscles of the participants in both groups.
- 5. To objectively determine the degree of range of ankle dorsiflexion mobility with full knee extension of the patients participating in the study.

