Recovery from painful injuries is associated with fear of movement, also known as kinesiophobia (24). It could be defined as an irrational or excessive fear of movement due to fear of injury or re-injury. For this reason, a kinesiophobia questionnaire (annex II) will be provided at the beginning of the study (day I, evaluation and first intervention) to all participants to assess kinesiophobia of performing certain movements that may cause pain or worsen previous injuries. It consists of 11 questions with a minimum score of 11 and a maximum of 44.

3. Ankle dorsiflexion range with the knee straight.

The evaluation of this variable will be carried out by measuring the angle obtained from the dorsiflexion of the ankle with a knee extension. This stretch is commonly performed in sports practice, so patients are generally already familiar with it...Stretching will be done with participants barefoot.. Likewise, participants will be instructed on how to place the test.. The leg to be tested was positioned so that the foot was placed on the midline of an area marked on the floor, and the foot of the healthy leg was placed forward at a distance of one step. The end point of the gastrocnemius stretch was defined as the point at which participants felt discomfort without lifting the heel and without pelvic rotation. Patients would place their hands against the wall for balance and would be asked to maintain the extended position of the hip and knee joints during the stretch (25).

. .

During the stretch, participants will be instructed to reach a pain or discomfort level of 7 or greater on a scale of 0 to 10 and therefore to hold the stretch at approximately this perceived intensity.

A digital camera (Canon EOS 2000D 24.1 MP) will be placed on the ground at a distance of 2 meters perpendicular to the plane of movement of the right leg to record the standing ankle dorsiflexion angle. The ankle joint angle in stretching will be analyzed by reflective markers placed on the knee (fibular head), ankle (external malleolus) and fifth metatarsal (head) and calculated by free software (RULER- Ergonauts Software. Polytechnic University of Valencia). The maximum standing dorsiflexion is defined as the intersection of a line joining the knee and ankle markers and the horizontal line crossing the heel and fifth metatarsal. (25)

4. Muscle fatigue of the triceps surae.

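### A three-arm trial with five unranked outcomes is to be analysed with two-group tests at 5% each; if any one significant result counts, the risk of a false benefit over sham is about 13–21%

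*Protocol*

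**What the plan says.** Section 5.A describes a randomised trial "with three parallel groups, prospective, longitudinal and with a blind evaluation for the researcher". Section 5.E confirms the arms: high intensity, low intensity and sham.

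Section 5.F gives the comparisons. For continuous outcomes: "For the comparison of means of the continuous dependent variables, a bivariate statistical analysis will be performed using the Student T test". For ordinal outcomes, "a comparison of medians will be performed using the bivariate analysis applying the Mann-Whitney test". The error level follows: "In all cases, a 95% confidence interval and a precision error of 5% will be established". No method for three groups is named.

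Section 4 asks "how effective is percutaneous electrolysis in terms of pain, kinesiophobia, fatigue and mobility", with the four domains side by side. Its hypothesis is that the high and the low intensity "will be more effective in the treatment of muscle tears of the internal calf than the simulated application of percutaneous electrolysis in adult subjects"; it names no outcome. Specific objective 4 is worded for two groups: "To demonstrate whether there are differences in muscle fatigue of the affected muscles of the participants in both groups".

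Sections 5.D and 6 give five scores of equal standing: pain standing, pain in contraction, TSK-11SV, dorsiflexion angle and heel-raise fatigue. None is called primary.

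**The concern.** The named tests compare two groups, while the design has three. Each of the five outcomes gives two contrasts with sham, so the hypothesis can be read against ten tests, each at 5%. The protocol neither says nor rules out that one significant result among them would support it.

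The deciding outcome and contrast can therefore be picked after the results are known, and the 5% level then no longer describes the risk of a false claim of benefit. Details of adjustment could properly sit in a statistical analysis plan that is not at hand. The primary outcome and a comparison that fits three arms define what the trial tests, and they belong in the protocol.

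**Working it through.** The protocol gives no power or overall error figure, so there is none to reproduce.

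**Inputs from the protocol**
- Three arms (5.A, 5.E) and about 50 participants (5.C).
- Two active-versus-sham contrasts (hypothesis, section 4).
- Five outcomes (5.D, section 6) and one post-treatment assessment, at day 28 (5.E).
- 5% per test (5.F), read as two-sided because it stands beside a 95% interval. That is 2.5% in the direction of benefit.

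**Assumptions not in the protocol**
- Arms of 17, 17 and 16.
- Independent-samples, pooled-variance t tests on normal outcomes.
- A common correlation between outcomes of 0, 0.3, 0.5 or 0.7.

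**Number of outcomes.** Section 5.D mentions TSK-11SV only at the start: "a kinesiophobia questionnaire (annex II) will be provided at the beginning of the study (day I, evaluation and first intervention) to all participants". However, the data sheet has a post-intervention field for it, section 5.E repeats all tests at day 28, and objective 3 compares the protocols on it. Five is the better reading; four is shown as well.

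**Step 1: reference values.** Ten independent tests would give 1 − 0.975^10 = 22.4%. This is slightly too high because the two contrasts share the sham arm. By simulation, one outcome with two active-versus-sham tests gives 4.51%. Five uncorrelated outcomes then give 1 − (1 − 0.0451)^5 = 20.6%.

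**Step 2: correlated outcomes, neither dose works.** By simulation (200,000 trials per setting). The second and third rows count only results in which an active arm is significantly better than sham.

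| Outcome correlation | 0 | 0.3 | 0.5 | 0.7 |
|---|---|---|---|---|
| At least one false benefit, five outcomes | 20.6% | 18.1% | 15.8% | 13.1% |
| At least one false benefit, four outcomes | 16.9% | 15.4% | 13.6% | 11.4% |
| Any false difference between any two arms, either direction, five outcomes | 47.8% | 44.9% | 39.8% | 33.2% |

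A large-sample normal calculation agrees for the second row: 20.7%, 15.7% and 12.8% at correlations of 0, 0.5 and 0.7. At a correlation of 0.9 the second row falls to 9.0%.

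**Step 3: the stricter rule, both doses must beat sham on the same outcome, any of the five.** The second row below is the chance of wrongly crediting the idle dose when the other improves all five outcomes by 1 SD.

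| Outcome correlation | 0 | 0.3 | 0.5 | 0.7 |
|---|---|---|---|---|
| Neither dose works | 2.4% | 2.3% | 2.1% | 1.8% |
| One dose works, the other does nothing | 11.9% | 10.4% | 9.1% | 7.6% |

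The second row (50,000 trials per setting) can be checked at correlation 0. If the working dose is significant on every outcome, the idle dose has five chances at 2.5%: 1 − 0.975^5 = 11.9%. With a single outcome and a large effect, the simulated figure is 2.6%.

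**Step 4: what the repair does to the detectable difference (80% power).** The standard error of a contrast, in SD units, is √(1/17 + 1/16) = 0.348. The detectable difference is the value at which a non-central t exceeds the critical value with probability 0.80.
- Unadjusted pairwise t, 31 df: 1.01 SD.
- Three-arm model with Dunnett critical value 2.28, 47 df (0.027 per comparison): 1.09 SD.
- Both doses must win, solved by simulation: 1.11 SD.
- Dunnett with baseline adjustment, residual SD √(1 − r²), 46 df: 1.04, 0.94 and 0.78 SD for assumed baseline correlations r of 0.3, 0.5 and 0.7.

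**The case against.** **The headline depends on a rule that the protocol does not state.** The hypothesis joins the two intensities, and on that reading the error when neither dose works is 1.8–2.4%. This is true, and it is why the 13–21% is given conditionally. It does not rescue the plan: the outcome is still left open, and the joint rule fails when only one dose works. That scenario is itself an assumption, but testing two intensities allows for it.

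**The range and the comparator are selective.** The range assumes correlations up to 0.7; at 0.9 the figure is 9.0%. Two contrasts on one outcome already give about 4.5% rather than 2.5%. Both points stand as qualifications. Even 9.0% is twice 4.5%.

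**Pairwise tests in three arms can be valid, and an unseen analysis plan may hold an adjustment.** Both are fair. Pairwise t or Mann-Whitney tests do estimate the two contrasts with sham. What remains is that this document fixes two-group tests at 5% throughout while naming no deciding outcome or contrast.

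**The text leaves some readings open.** Section 5.F does not say which groups or times the t test compares, and objectives 1 and 2 are worded arm by arm, so a within-arm use is possible; the percentages above would not describe it. Mann-Whitney, which needs independent groups, and objectives 3 and 4 support a between-arm reading. Taking the 5% as a significance level is also an inference, though the natural one. The two-group wording of objective 4 may be only a slip and is weak evidence.

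**Conclusion.** The concern holds and should be corrected before the data are analysed. The firm part needs no simulation: three arms, five outcomes of equal rank, only two-group tests, and no rule for what would support the hypothesis. The size depends on the rule eventually applied. If any single result counts and neither dose works, the risk of a false benefit is about 13–21%, or 11–17% with four outcomes. If both doses must win on a shared but unnamed outcome, it is about 2% when neither works and 8–12% when only one does. All these figures rest on near-equal arms, between-arm tests and outcome correlations of 0 to 0.7, none of which the protocol states.

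**What to change.** In section 5.F:

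1. Name one outcome already collected as primary at day 28, for example pain in contraction.
2. Replace the two-sample tests with one three-arm model, preferably adjusted for the baseline score already recorded, and report high versus sham and low versus sham.
3. State one success rule: (a) either dose may succeed, with a Dunnett or equivalent adjustment; or (b) both doses must beat sham on the primary outcome, with no adjustment between arms.
4. Label the other outcomes and the high-versus-low contrast as secondary, reported as estimates with confidence intervals.

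In section 4, reword objective 4 to refer to all three groups.

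The cost is a few sentences and no extra patients. There is a modest loss of sensitivity on the primary outcome: from about 1.01 SD to 1.09 SD under (a) or 1.11 SD under (b), with all 50 participants analysed and no dropout. Under (a), baseline adjustment would offset part or all of this, depending on a baseline correlation that the protocol does not give.
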